8.2.2. Exclusion criteria

Patients meeting any of the following criteria will not be included in the study:

1. Patients that initiated HER2 inhibitors.

8.3. Variables

The following variables will be collected from the MHS electronic database and non-structured data extracted from PDF files of patient data:

Variable	Source	Role in study	Period of measurement	Reporting phase	Operational definition
Demographic and Clinical and health related characteristics at baseline					
PatID	MHS structured data	Data linkage		Not reported	Unique patient identifier used to link clinical records. This information will not be disclosed to the study sponsor.
Gender	MHS structured data	Baseline characteristic	Prior medical history	Reported	Male/Female
Age	MHS structured data	Baseline characteristic	Baseline	Reported	Patient's age (in years) at index date.
Age groups	MHS structured data	Baseline characteristic	Baseline	Reported	Groups such as <50 versus ≥ 50
Body mass index (BMI)	MHS structured data	Baseline characteristic	Baseline	Reported	Median (Interquartile Range - IQR)
BMI groups	MHS structured data	Baseline characteristic	Baseline	Reported	Underweight (BMI < 18.5), normal (BMI 18.5-24.9), overweight (BMI 25-25.9), obese (BMI ≥ 30), missing
Smoking history	MHS structured data	Baseline characteristic	Baseline	Reported	Ever smoker, never smoker, unknown.

Menopausal status	MHS structured data	Baseline characteristic	Baseline	Reported	Pre-, peri- or post-menopausal
Region of residence	MHS structured data	Baseline characteristic	Baseline	Reported	North, South, Central region
Socioeconomic status	MHS structured data	Baseline characteristic	Baseline	Reported	Based on a points system, categorized as low (1-4), medium (5-6), high (7-10)
Co-morbidities	MHS validated registries	Baseline characteristic	Baseline	Reported	For cardiovascular disease, cerebrovascular disease, stroke, congestive heart failure, diabetes mellitus, chronic kidney disease, hypertension, Chronic obstructive pulmonary disease (COPD).
Variable	Source	Role in study	Period of measurement	Reporting phase	Operational definition
Chronic diseases	MHS structured data	Baseline characteristic	Baseline	Reported	Depression as defined by ICD-9 codes.
Deyo-Charlson Comorbidity index	MHS structured data and MHS validated registries	Baseline characteristic	Baseline	Reported	
Co-medications	MHS structured data	Baseline characteristic	Baseline	Reported	At least 2 purchases within 3 months prior to index date.
Genetic counselling for gBRCAm (germline Breast Cancer gene mutation)	MHS structured data	Baseline characteristic	Baseline	Reported	yes/no

Genetic testing for gBRCAm performed	MHS structured data	Baseline characteristic	Baseline	Reported	yes/no
Death	MHS structured data	Endpoint	After index date		Death is captured from National Insurance Data
Disease Characteristics					
Date of initial breast cancer diagnosis	National cancer registry	Baseline characteristic	Baseline	Reported	Records may be incomplete
Histology	Extracted from PDF patient data files	Baseline characteristic	Baseline	Reported	
Location of metastases	Extracted from PDF patient data files	Baseline characteristic	Baseline	Reported	Bone, brain, lymph nodes, ovary, visceral
Visceral/non visceral status	Extracted from PDF patient data files	Baseline characteristic	Baseline	Reported	Non-visceral, visceral (lungs, liver), bone only
Eastern Cooperative Oncology Group (ECOG) performance status at diagnosis	Extracted from PDF patient data files	Baseline characteristic	Baseline	Reported	Grouped as 0-1, 2, 3-4, unknown/missing
Molecular status data: performed HER2/ HR tests	Extracted from PDF patient data files	Baseline characteristic	Baseline	Reported	yes/no
Hormone sensitivity	Extracted from PDF patient data files	Baseline characteristic	Baseline	Reported	primary or secondary resistance
Variable	Source	Role in study	Period of measurement	Reporting phase	Operational definition
Progression of disease from imaging	Extracted from PDF patient data files	Baseline characteristic	Baseline	Reported	
Treatment Characteristics					

Index treatment regimen	MHS structured data	Treatment characteristic	Study observation period	Reported	Palbociclib combination treatment - combination with aromatase inhibitor or fulvestrant.
Lines of therapy	MHS structured data and PDF patient data files.	Treatment characteristic	Study observation period	Reported	Identified according to the sequence of dispensed medications.
Median duration of each line of therapy	MHS structured data	Treatment characteristic	Study observation period	Reported	Duration in weeks or months between the start and stop of each line of therapy will be reported as mean (SD) and median (IQR)
Number of cycles of index treatment	MHS structured data	Treatment characteristic	Study observation period	Reported	Mean (SD) and Median (IQR)
Index palbociclib treatment dose	MHS structured data	Treatment characteristic	Study observation period	Reported	Mean (SD) and Median (IQR)
Index palbociclib treatment dose schedule change	MHS structured data	Treatment characteristic	Study observation period	Reported	Proportion of patients with dose changes
Date of treatment initiation	MHS structured data	Treatment characteristic	Study observation period	Not Reported	First date will be used if a regimen consists of more than one drug given on different dates.
Index treatment end date	MHS structured data	Treatment characteristic	Study observation period	Not Reported	Date of final treatment for each drug or regimen. It is possible that the patient's treatment stop date is not documented if the patient dies, is lost to follow up or is still on therapy. The final treatment date death date or end of

					study date will be used, whichever is earliest.
Variable	Source	Role in study	Period of measurement	Reporting phase	Operational definition
Post-palbociclib treatment duration	MHS structured data	Clinical Outcomes	Study observation period	Not Reported	
The regimen received by patients following discontinuation from the palbociclib treatment.
 
The duration (in weeks) between the start and stop of the post-palbociclib treatment. Findings will be summarized as the mean (\pm SD) and median (range) of values.

					subsequent treatment for unknown reasons
Time to chemotherapy after palbociclib treatment	MHS structured data	Clinical Outcomes	Study observation period	Reported	Time to chemotherapy (Kaplan Meier method median (95% CI)) from end of index treatment and start of chemotherapy. Summary of number of events and censored patients at 6, 12, 18, 24 months.
Time to next treatment (TTNT)	MHS structured data	Treatment characteristic	Study observation period	Reported	TTNT will be defined as the interval (in weeks or months) between the start of the index treatment date and the date of the next-line treatment. Patients who did not advance to the next treatment will be censored on the study end date or death, whichever occurs first. Kaplan-Meier (K-M) method with 95% CI and summary tables of

					events and censored patients at 6, 12, 18, 24 months.
CCI					

8.3.1. Demographic characteristics at baseline (from structured electronic database):

- Patient demographics: age, age group and gender.
- Region of residence (North, Central, South).
- Socioeconomic status (SES): based on a score ranked with 1 (lowest) to 10 derived for commercial purposes by Points Location Intelligence using geographic information systems (GIS) and data such as expenditures related to retail chains, credit cards and housing. This score is highly correlated with SES measured by the Central Bureau of Statistics¹. SES will be categorized into low (1-4), medium (5-6) and high (7-10).

8.3.2. Clinical and health related characteristics at baseline:

- Body mass index (BMI) will be categorized using standard cut-points ².
- Baseline chronic diseases will be identified using previously validated MHS automated chronic disease registries for the following co-morbidities: diabetes ³, cardiovascular disease (CVD) ⁴, chronic kidney disease (CKD) ⁵, hypertension ⁶, COPD, other patient relevant condition (if applicable) e.g. depression.
- Deyo-Charlson Comorbidity index (using validated MHS patient registries where available).
- Co-medications – Minimum of 2 purchases within the 3 months period prior to index date.
- Menopausal status.

- Cancer history will be obtained from National Cancer Registry ⁷ data available through 2015 and MHS cancer registry data which draws from pathology reports and diagnoses linked to cancer medication approvals through 2017.
- Smoking status (ever/never/unknown) will be obtained from the MHS database and/or physician reports.
- Genetic counselling for germline BRCA mutation carried out yes/no.
- Testing for germline BRCA mutation carried out yes/no.

8.3.3. Treatment patterns:

- Number (N) (%) patients receiving first, second- and third-line treatments by drug name and therapeutic group, median duration of each line of therapy, and number of cycles for each line of therapy. Treatment lines are defined according to the sequence of dispensed medications, with information captured both from pharmacy database (for medications approved by the HMO), and from hospital medical records (including information on medications provided by private insurance and clinical studies) using the following algorithm. Any drug purchased within 1 month of a new line is considered part of that line. Cessation of a drug from a combination regimen is considered the same line as the patient is not receiving additional treatment. Cessation is likely due to tolerance issues or adverse effects although we do not know the reason as our data is from purchase data. Addition of a new drug to a current regimen is considered a new treatment line.
- Index treatment regimen - palbociclib combination partner: Aromatase Inhibitors (AI) or fulvestrant; Subsequent therapy per lines of therapy.
- Dosing and dose changes, interruptions, delays, and discontinuations associated with palbociclib therapy.
- Treatment lines will be rerun for extended follow up to 30 June 2022.

8.3.4. Cancer related variables:

These variables will be extracted from patient PDF files/ letters sent to MHS from the physician.

- Date of initial breast cancer diagnosis.
- Histology.
- Location of metastases: bones, brain, visceral, lymph nodes, other.

- ECOG performance status at diagnosis.
- Molecular status data: performed HER2/ HR tests (yes/no).
- Hormone sensitivity: primary or secondary resistance.
- Progression of disease from imaging.

8.3.5. Clinical outcomes for palbociclib (analysed separately by therapy line):

- N (%) progression at 6, 12 and 24 months.
- Duration of treatment on palbociclib (Median time on treatment).
- Time on treatment for subsequent line of therapy.
- Time to chemotherapy after palbociclib treatment.

■ CCI [REDACTED]

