6. RATIONALE AND BACKGROUND

Breast cancer is a major cause of mortality in females worldwide. Hormone receptor positive (HR+) and human epidermal growth factor receptor 2 negative (HER2-) breast cancer is the most commonly diagnosed subtype accounting for around 75% of all diagnosed breast cancers¹. Palbociclib is a first in class cyclin-dependent kinase 4 and 6 (CDK4/6) inhibitor that has been approved for use in HR+/HER2- advanced/ metastatic breast cancer (ABC/ MBC) patients in a number of indications on the basis of efficacy demonstrated in 3 pivotal clinical trials; PALOMA-1 and PALOMA 2 (initial endocrine-based therapy) and PALOMA-3 (after progression following endocrine therapy) ^{2,3}. As a result of the recent approvals there is a need to understand the real world usage and clinical outcomes of patients receiving CDK4/6 inhibitors, including palbociclib, in order to inform future treatment decisions.

There is high level of screening and awareness for breast cancer in Israel. Palbociclib was included in the national health basket and therefore reimbursed since January 2018 in all lines of treatment, according to the labeling.

Although there is Real-World Evidence (RWE) on palbociclib published from the USA, Argentina, Germany and Italy ^{4,5,6} there is no awareness of RWE with palbociclib coming from Israel.

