8. RESEARCH METHODS

8.1. Study design

This is a population based retrospective database study that will include patients with metastatic, HR+/ HER2- breast cancer and who initiated first or subsequent lines of treatment with palbociclib. Data will be available from Maccabi Healthcare Services (MHS) database in Israel for patients who received approval for treatment with palbociclib since 01 January 2018 until 31 August 2020.

Treatment amendment and extension: Treatment lines will be rerun for the same patient cohort for an additional year and a half of follow-up to 30 June 2022.

The database review followed by a medical record review will capture data from approximately 500-700 patients on demographics, clinical characteristics, disease history, treatment history, palbociclib dosing, clinical outcomes and post-palbociclib combination therapy treatment data. The study will be descriptive in nature therefore no control or comparator groups will be included.

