8.2.1. Inclusion criteria

Patients must meet all of the following inclusion criteria to be eligible for inclusion in the study:

1. A diagnosis of metastatic breast cancer, based on the National/MHS cancer registry.
2. Newly diagnosed metastatic breast cancer patients and newly treated with palbociclib within 6 months of diagnosis, in any line of treatment in the metastatic setting.
3. Available data on palbociclib treatment for at least 6 months.
4. Continuous healthcare plan enrolment in MHS for at least one year before index date.
5. At least 18 years of age at index date.

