8.7. Data analysis

Data will consist of structured data from the MHS electronic database and non-structured data extracted from PDF files of patient data. Data validation will be performed and consist of quality control checks for appropriate values, logical sequences and quantity of missing values. Missing data will be identified and reported in the results tables as percentages for all variables. If there is a large amount of missing or illogical data, a decision to include, exclude or impute that variable will be subsequently made based on the study sponsor's decision.

Descriptive analyses will be conducted to evaluate the demographic, clinical and treatment characteristics overall, as well as for each of the study cohorts. Results will be reported in aggregate. Categorical variables (eg, ECOG performance status) will be reported as frequency and percentage. Continuous variables such as age will be reported as mean, (standard deviation) and median (Inter quartile range). In the case of missing observations, the number and percentage of missing values will be reported. Chi-square testing will be used to assess associations between categorical variables when patient counts for single cells within the results tables are greater or equal to 5. When distribution cannot be assumed to be Chi-square, then Fisher's exact test will be used. Depending on normality, analysis of variance (ANOVA)/t-tests or Kruskall-Wallis tests will be used for continuous variables. An alpha level of 0.05 will be the primary criterion for statistical significance of this study.

Time from treatment initiation until progression (as determined in the patient record) and drug discontinuation will be determined for the calculation of median time on treatment.

Duration of treatment on palbociclib, Time on treatment for subsequent line of therapy and Time to chemotherapy after palbociclib treatment and **CCI**

Plots will be generated. Patients are censored at end of study or left MHS.

Sub- analyses will be carried out for palbociclib.

All analyses will be conducted using IBM SPSS Statistics for Windows, Version 22.0. Armonk, NY: IBM Corp, and a P value < 0.05 is considered statistically significant.

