ANNEX 1. LIST OF STAND ALONE DOCUMENTS

1. Baseline demographic and clinical characteristics of patients diagnosed with metastatic breast cancer 2018-2019 split by Palbociclib as first-, second- or third line (n=XX).

		First Line	Second Line	Third Line	Total n=XXX

Demographic Variables					
Age	median (IQR)				
	<65				
	≥65				
Gender	male				
	female				
Region of residence	Central				
	North				
	South				
Socioeconomic status*	low				
	medium				
	high				
Clinical Variables					
Deyo-Charlson Comorbidity Index (without malignancy or HIV)	mean (SD)				
	0				
	1				
	2				
	3				
	≥4				
Co-morbidities	Diabetes mellitus				
	Cardiovascular disease				
	Stroke				
	Congestive heart failure				
	Hypertension				
	Chronic kidney disease				

	Chronic obstructive pulmonary disease			
	Other (e.g. depression)			
Co-medications				
Smoking	Ever smoker			
	Never smoker			
	Unknown			
BMI				
Menopausal status	Pre/Peri menopausal			
	Postmenopausal			
Genetic counselling for gBRCAm	Yes			
	No			
Testing for gBRCAm	Yes			
	No			

2. Cancer related characteristics of patients with breast cancer at baseline

		First Line	Second Line	Third Line	Total (n)
Histology					
Location of metastases	Brain				
	Bone				

	Visceral				
	Lymph nodes				
	Other				
ECOG	0-1				
	2				
	3-4				
	Unknown/missing				
Hormone sensitivity	Primary				
	Secondary				
Molecular status data: performed HER2 / HR tests	HR+ [Estrogen Receptor positive (ER+), Progesterone Receptor positive (PR+) or both]				
	HER2+				

3. Time on Palbociclib treatment

Line of treatment (first-, second- or third line)	N	Number (%) discontinued	Median time on treatment (95% CI), months	% on treatment at 3 months	% on treatment at 6 months	% on treatment at 12 months	% on treatment at 24 months	Log rank P value

4. Palbociclib treatment patterns

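### Hormone sensitivity offers only two categories, both of them resistance, although patients with no prior endocrine therapy or no resistance are eligible

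*Combined protocol and SAP*

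**What the plan says.** Hormone sensitivity is listed in the section 8.3 variables table as a reported baseline characteristic, taken from the PDF patient files. Its operational definition reads in full "primary or secondary resistance". Section 8.3.4 has the same content: "Hormone sensitivity: primary or secondary resistance". In Annex 1, the second table shell (cancer-related characteristics at baseline) carries a "Hormone sensitivity" block with two rows, Primary and Secondary, under First Line, Second Line, Third Line and Total. Neither term is defined anywhere in the document.

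On the population, section 8.1 covers patients "who initiated first or subsequent lines of treatment with palbociclib". Inclusion criterion 2 in section 8.2.1 takes newly diagnosed metastatic patients "newly treated with palbociclib within 6 months of diagnosis, in any line of treatment in the metastatic setting". The only exclusion criterion concerns HER2 inhibitors.

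On missing values, ECOG status has its own residual level ("Grouped as 0-1, 2, 3-4, unknown/missing"). Hormone sensitivity has none, but section 8.7 gives a general rule: "Missing data will be identified and reported in the results tables as percentages for all variables".

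**The concern.** A variable named for sensitivity has no value that means sensitive, and none for a patient who has never had endocrine therapy. A patient without endocrine exposure cannot have shown resistance of either kind, so the list is not exhaustive for the cohort that the protocol itself defines.

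The primary objective is to describe the characteristics of patients starting palbociclib in every line. In a descriptive study the baseline tables are part of the deliverable. At stake is whether a reader of the second Annex 1 table can tell how much of each line was endocrine-resistant, how much was not, and how much was simply undocumented. The variable comes from manual reading of letters, so a level left out at abstraction is more costly to add later than before the reading starts.

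**Working it through.** The plan gives no figure to reproduce, and no power or precision formula applies. The check compares the category list with the eligible population, then asks what the resulting table could tell a reader.

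**Step 1: is the short list an isolated slip?** No. The variables table in 8.3, the list in 8.3.4 and the Annex 1 shell agree on the same two values.

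**Step 2: can an eligible patient fall outside both values?** Yes.
- Section 8.1 and inclusion criterion 2 admit first-line use in newly diagnosed metastatic disease.
- No criterion in 8.2, 8.2.1 or 8.2.2 asks for earlier endocrine therapy or for resistance to it.
- Section 6 separates trials of initial endocrine-based treatment from the trial after progression on endocrine therapy, so the protocol recognises both settings.

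Two kinds of eligible patient therefore have no value: those with no prior endocrine therapy, and those previously treated without resistance.

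**Step 3: where would they go?** The plan gives abstractors no instruction. If the two values are applied honestly, the field stays blank, and section 8.7 then reports the blank as missing.

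**Step 4: what could the table show?** In one column with n patients, let r1 and r2 be the numbers with primary and secondary resistance, s the number sensitive or never treated, and u the number undocumented, so that n = r1 + r2 + s + u. The table shows r1, r2 and the blanks m = s + u. It does not show s and u separately. The share resistant among patients with a documented status is

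(r1 + r2) / (n − u).

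- If no blank is undocumented (u = 0), this is (r1 + r2)/n = 1 − m/n.
- If every blank is undocumented (u = m), it is (r1 + r2)/(r1 + r2) = 100%.

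The same table fits any value between these limits. For assumed blank shares, used only for illustration:

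| Assumed blank share m/n | Resistant share compatible with the table |
|---|---|
| 20% | 80% to 100% |
| 50% | 50% to 100% |
| 70% | 30% to 100% |

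**Step 5: how many patients?** Section 8.5 expects about 500 to 700 patients. The share who are sensitive or never treated is not given, so the range below is an assumption. Number without a valid value = share × N.

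| Assumed share | N = 500 | N = 700 |
|---|---|---|
| 20% | 0.20 × 500 = 100 | 0.20 × 700 = 140 |
| 50% | 0.50 × 500 = 250 | 0.50 × 700 = 350 |
| 70% | 0.70 × 500 = 350 | 0.70 × 700 = 490 |

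These figures show scale only. The gap in the list does not depend on them.

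**The case against.** The strongest reply is that section 8.7 already deals with patients who have no value: they appear in a reported missing percentage and do not vanish. Menopausal status and visceral status also lack an unknown level and rely on the same rule, so the contrast with ECOG proves little. This stands as far as it goes. What it does not answer is the pooling in step 4: a known clinical state would be reported as absent data. Section 8.7 also allows a variable with much missing data to be included, excluded or imputed at the sponsor's decision, and that rule could then be triggered by values that are not truly missing.

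A reader might infer something stronger: that non-resistant patients will be forced into a resistance class, that resistance will be overstated, and that the loss is permanent. The documents do not support this.
- No text makes the field mandatory or tells abstractors to choose a class by default, and the abstraction form itself is not in the documents.
- No text fixes the denominator. On the full column n, the two rows need not sum to 100% and resistance is not inflated.
- At least partial repair is possible. Sections 8.3.3 and 8.4 describe dispensing data and hospital records, and section 8.6.2 keeps source documents for at least 15 years. The repair may be incomplete, because only one year of enrolment before index is required and dispensing alone does not show resistance.

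Nor can one infer that most first-line patients are affected. Newly diagnosed metastatic disease does not exclude recurrence after earlier endocrine treatment. The documents show that such patients are eligible, not how many there are.

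Finally, this is one descriptive variable. It is not an eligibility criterion, an outcome in 8.3.5 or a column split in Annex 1. That limits the consequence and is accepted.

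**Conclusion.** The point holds in limited form. The stated categories do not cover the eligible cohort. Followed as written, the plan would most likely merge patients who are not resistant, or to whom the question does not apply, with patients whose status is undocumented. The Hormone sensitivity rows would then be hard to interpret, most of all under First Line.

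The number of patients concerned is not derivable from the documents. The conclusion rests on two things: eligibility does not require prior endocrine exposure, which the text shows, and abstractors would leave the field blank when neither value fits, which is the likeliest reading but is not stated. No visible endpoint analysis is affected. If the tests for categorical variables in section 8.7 were applied to this variable across lines, they would compare only the classified patients.

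The change is worth making because it is cheap and the variable is already planned for reporting.

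**What to change.** In section 8.3, section 8.3.4 and the second Annex 1 table, use five levels, assessed at the index date:

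1. No prior endocrine therapy (including de novo metastatic patients without earlier endocrine treatment)
2. Endocrine-sensitive (prior endocrine therapy without resistance)
3. Primary resistance
4. Secondary resistance
5. Unknown or not documented

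Keep the first two apart, since never exposed and exposed without resistance are different states. State the definition of primary and secondary resistance that abstractors are to apply. Report percentages on the full column n, so that the five rows account for every patient in each line.

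If abstraction is already complete, re-classify the blank values from dispensing data and the retained letters, and report how many remain unknown.

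The cost is three more options in the abstraction form, three more table rows and a short definition. If the charts have been read, add the time to re-abstract the blanks. No new data source is needed.

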8.6. Data management

Part of the data will be collected from the main database, such as demographics, comorbidities, systemic therapy (not including chemotherapy like cisplatin or carboplatin), date of death. Data that is not available in the main database such as tumor characteristics (stage of disease, histology), chemotherapy (cisplatin, carboplatin), response (from imaging results), biomarker status, metastases site, Eastern Cooperative Oncology Group (ECOG) results, and discontinuation will be extracted through additional chart review from medical letters in PDF format by trained data extractors. Extracted data will be recorded in an electronic case report form created for this study using Microsoft Access Database. All data is anonymous and does not leave the MHS system.

SPSS version 24 and R data processing and statistical software will be used.

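### The line-duration rows in section 8.3 use plain means and medians and do not apply the censoring in 8.7, so unfinished palbociclib and later lines would be summarised as too short

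*Combined protocol and SAP*

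**What the plan says.** All references are to the combined protocol and SAP.

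- **Section 8.3, line-duration row (marked as reported).** "Duration in weeks or months between the start and stop of each line of therapy will be reported as mean (SD) and median (IQR". The row gives no censoring rule and does not mention Kaplan-Meier.
- **Section 8.3, post-palbociclib duration row (marked as not reported).** Start-to-stop time in weeks, summarised by plain mean (SD) and median (range).
- **Section 8.3, index end-date row.** A stop may be undocumented because the patient dies, "is lost to follow up or is still on therapy. The final treatment date death date or end of" study is then used, whichever is earliest. No event/censor indicator is attached. The rule is written for the index treatment. The visible text has no equivalent for later lines, although table text may have been lost at that point.
- **Section 8.7.** Palbociclib duration and time on the subsequent line are listed, followed by a redaction, plots and "Patients are censored at end of study or left MHS". The general rule for continuous variables in the same section is again mean (SD) and median (IQR).
- **Time-to-event handling elsewhere.** The TTNT row uses Kaplan-Meier: "Patients who did not advance to the next treatment will be censored on the study end date or death, whichever occurs first". Annex 1, Table 3, for palbociclib, asks for "Number (%) discontinued", "Median time on treatment (95% CI), months", percentages on treatment at fixed times and a log-rank P value.
- **Section 8.6.** Among items not held in the main database, tumour characteristics and others "and discontinuation will be extracted through additional chart review from medical letters in PDF format by trained data extractors".

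**The concern.** Patients started palbociclib up to 31 August 2020 and treatment lines are followed to 30 June 2022, so some lines will still be running at the cut-off. If the cut-off or last purchase date serves as the stop date, the recorded duration is a lower bound, and a plain mean or quantile treats it as a completed duration. Later lines are more exposed because they start later and have less follow-up left.

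Treatment patterns are part of the primary objective, duration per line is listed among them in 8.3.3, and the extension to June 2022 reruns the treatment lines. An analyst who follows the 8.3 rows and one who applies the 8.7 rule would report different durations from the same data.

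Death on treatment is also unsettled. It is an end date in the index row, a censoring time for TTNT, and is not named in the visible 8.7 rule.

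**Working it through.** The plan states no expected duration, event count or sample-size calculation, so it has no figure to reproduce. The check is what the rows would return under stated assumptions.

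**Inputs from the documents.** Entry runs from 1 January 2018 to 31 August 2020 (8.1), about 32 months. The cut-off is 30 June 2022 (8.1, 8.3.3). Potential follow-up from index is therefore about 22 to 54 months. Loss from MHS is under 1% a year (8.4) and is ignored.

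**Assumptions.** Entry is uniform, so follow-up C is uniform on 22 to 54. Time on a line, T, is exponential with median m and rate λ = ln 2 / m. The date at cut-off is used as the stop, so the recorded time is min(T, C). The six-month treatment-data criterion is not modelled.

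**Palbociclib line, formulas.**

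- Share ongoing: p = (e^(−22λ) − e^(−54λ)) / (32λ)
- Plain mean: (1 − p)/λ; true mean: 1/λ
- A plain quantile x solves e^(−λx) × min(1, (54 − x)/32) = 1 − q

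For x up to 22 the second factor is 1, so a quantile is distorted only when its true value exceeds about 22 months.

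**With m = 20.** λ = 0.03466.

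- p = (0.4665 − 0.1539)/1.109 = 0.282
- Plain mean = 28.85 × 0.718 = 20.7; true mean = 28.9
- Median = 20.0, unchanged
- Upper quartile: at x = 30.76, 0.344 × 0.726 = 0.25, so 30.8 against a true 40.0 (30.7 with follow-up of 21.9 to 53.9 months from the exact dates)

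| True palbociclib median (months) | Ongoing | Mean: true / plain | Upper quartile: true / plain | Plain median |
|---|---|---|---|---|
| 10 | 9% | 14.4 / 13.2 | 20 / 20.0 | 10.0 |
| 12 | 13% | 17.3 / 15.1 | 24 / 23.3 | 12.0 |
| 15 | 19% | 21.6 / 17.6 | 30 / 26.6 | 15.0 |
| 20 | 28% | 28.9 / 20.7 | 40 / 30.8 | 20.0 |
| 25 | 36% | 36.1 / 23.1 | 50 / 33.7 | 23.4 |

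**Next line (simulation).** The line starts when palbociclib ends, its duration is independent of palbociclib duration, and the palbociclib median is 15 to 24 months.

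| True next-line median (months) | Plain median | Kaplan-Meier median |
|---|---|---|
| 6 | 5.2–5.4 | 6.0 |
| 9 | 7.3–7.7 | 9.0 |
| 12 | 9.0–9.6 | 12.0 |

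At a true median of 9, 22–25% of next lines are ongoing and the plain mean is 9.7–10.1 against 13.0. If only finished lines were counted, the median would be 6.5–6.7.

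**Sensitivity.** Weibull shapes 0.8 to 1.3 were combined with uniform, front-loaded and back-loaded entry, with true medians of 20 (palbociclib) and 9 (next line). Between 16% and 37% of palbociclib lines are ongoing. The plain palbociclib mean is low by 24.5 − 21.8 = 2.7 months (11%) to 35.8 − 19.0 = 16.8 months (47%). The plain next-line median is 7.0–7.9.

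**Dependence between lines.** With a correlation of 0.3 between palbociclib and next-line durations (Gaussian copula, medians 20 and 9), the true next-line median is 9.0 in all patients and 7.7 among those who start a next line by the cut-off. Kaplan-Meier gives 7.5 and the plain median 6.3.

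**The case against.** The best defence is that 8.7 already covers this. It names both durations, promises plots and states a censoring rule, and a redaction sits where a method may have been named. The 8.3 row is an entry in a variable list; it is silent on censoring and does not forbid it. This stands in part: a reader might infer that the plan never censors durations, and the documents do not support that. But the visible 8.7 text does not refer to the 8.3 rows, its own general rule for continuous variables is the plain form, and the end-date row supplies a date without saying whether it is an event.

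A reader might also infer that the 8.3 row contradicts the TTNT row and Annex Table 3. It does not. TTNT runs from index start to the next line. Table 3 concerns time on palbociclib, which can differ from line duration: "Cessation of a drug from a combination regimen is considered the same line as the patient is not receiving additional treatment". Both only show that the plan uses time-to-event methods elsewhere.

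Two limits on size also stand. With the cut-off date as the stop, the palbociclib median is untouched up to a true value of about 22 months. The upper quartile is untouched when its own true value is below that, which under exponential times means a median up to about 11 months. Palbociclib may be given in any line, so durations that short are possible.

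**Conclusion.** The concern holds as a failure to align the two 8.3 duration rows with the 8.7 censoring. The direction is certain if the rows are followed literally: plain means are short whenever any line is unfinished, and later-line medians are short. Bias in the palbociclib upper quartile and median is conditional on the 22-month limit.

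The size rests on assumed durations, distribution and entry pattern, none of which the documents give. Over the cases examined, the palbociclib mean is understated by 11% to 47% at a true median of 20 months, and a true next-line median of 9 months is reported about 1 to 2 months short.

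Kaplan-Meier should not be read as always recovering the true later-line value. It does so here only when successive line durations are independent; under dependence it was still closer than the plain median. This should be fixed before the June 2022 rerun is reported. Confidence is medium, because of the redacted text in 8.7 and the possible loss of table text in 8.3.

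**What to change.** In both 8.3 duration rows:

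1. For the palbociclib line and all later lines, report Kaplan-Meier median and quartiles with 95% CI and numbers at risk. Censor patients still on the line at 30 June 2022 or who left MHS, as in 8.7.
2. Define a stop, for analysis purposes, from the dispensing sequence (last purchase or start of a new line), supplemented by chart discontinuation where available. State how a last purchase close to the cut-off is told apart from a true stop, and give the rule for later lines as well as the index treatment.
3. State how death on treatment counts, and use the same statement in 8.7.
4. Keep plain mean (SD) and median (IQR) only for lines completed before palbociclib. For other lines drop the mean, replace it with a restricted mean to a stated horizon, or label it as observed time only.

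The cost is a wording change, slightly more analysis work and wide intervals at late times. The dispensing data are already being rerun to June 2022. Chart discontinuation may not be available to that date, since the objectives and design sections extend only treatment patterns and lines; this is why the stop rule should rest on dispensing first.
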